5. GENERAL METHODOLOGY AND CONVENTIONS

5.1. Hypotheses and Decision Rules

Hypothesis testing will be used to assess the 2 primary immunogenicity objectives.

5.1.1. Pneumococcal Immunogenicity Hypotheses

The null hypothesis (H_{01}) for each pneumococcal serotype is

$$H_{01}: \ln(\mu_A) - \ln(\mu_B) \leq \ln(0.5)$$

where $\ln(0.5)$ corresponds to a 2-fold margin for the assessment of NI with respect to the immune responses to 20vPnC and

- $\ln(\mu_A)$ is the natural log of the serotype-specific OPA GMT 1 month after coadministration of SIIV and 20vPnC for the (SIIV+20vPnC)/saline group
- $\ln(\mu_B)$ is the natural log of the serotype-specific OPA GMT 1 month after 20vPnC administration for the (SIIV+saline)/20vPnC group.

NI for serotype-specific OPA titers for each serotype will be formally evaluated by a 2-sided 95% CI for the ratio of serotype-specific OPA GMTs ([SIIV+20vPnC]/saline group over [SIIV+saline]/20vPnC group) 1 month after vaccination with 20vPnC. The null hypothesis (H_{01}) will be rejected and NI for a serotype will be declared if the lower bound of the 2-sided 95% CI for the GMR of the (SIIV+20vPnC)/saline group to the (SIIV+saline)/20vPnC group is greater than 0.5 (2-fold criterion) for that serotype.

5.1.2. SIIV Immunogenicity Hypotheses

The null hypothesis (H_{02}) for each SIIV strain-specific antibody is

$$H_{02}: \ln(\mu_C) - \ln(\mu_D) \leq \ln(0.67)$$

where $\ln(0.67)$ corresponds to a 1.5-fold margin for assessment of NI with respect to the immune responses to SIIV and

- $\ln(\mu_C)$ is the natural log of the SIIV strain-specific HAI GMT 1 month after coadministration of SIIV and 20vPnC for the (SIIV+20vPnC)/saline group
- $\ln(\mu_D)$ is the natural log of the SIIV strain-specific HAI GMT 1 month after SIIV administration for the (SIIV+saline)/20vPnC group

NI for strain-specific HAI titers will be formally evaluated by a 2-sided 95% CI for the ratio of strain-specific HAI GMTs ([SIIV+20vPnC]/saline group over [SIIV+saline]/20vPnC group) 1 month after SIIV. The null hypothesis (H_{02}) will be rejected and NI for strain-specific HAI will be declared if the lower bound of the 2-sided 95% CI for the GMR of the coadministration group to the separate-administration group is greater than 0.67 (1.5-fold criterion).

CCI

5.2. General Methods

Time points for local reactions and systemic events refer to data within 10 days and 7 days, respectively, after each vaccination.

Prompted local reactions, prompted systemic events, and AEs will be summarized after each vaccination at Visit 1 and Visit 2 by vaccine group.

CI for all endpoints in the statistical analysis will be presented as 2-sided at the 95% level.

5.2.1. Analyses for Binary Data

Descriptive statistics for categorical variables (eg, proportions) are the percentage (%), the numerator (n) and the denominator (N) used in the percentage calculation, and the 95% CI where applicable.

The exact 95% CI for binary endpoints for each group will be computed using the F distribution (Clopper-Pearson).¹ The 95% CI for the between-group difference for binary endpoints will be calculated using the Miettinen and Nurminen² method.

The 3-tier approach will be used to summarize AEs. For both Tier 1 (if any are identified during the study) and Tier 2 events, a 95% CI for the between-group difference in proportions will be calculated based on the Miettinen and Nurminen method. In addition, for Tier 1 events (if any), the asymptotic p-values will also be presented for the difference in proportions, based on the same test statistic and under the assumption that the test statistic is asymptotically normally distributed. For Tier 3 events, counts and percentages for each vaccine group will be provided.

Between-group comparisons will be calculated for Tier 2 AEs specified as following:

- After vaccination with SIIV and 20vPnC for the (SIIV+20vPnC)/saline group vs after vaccination with SIIV and saline for the (SIIV+saline)/20vPnC group
- After vaccination with SIIV and 20vPnC for the (SIIV+20vPnC)/saline group vs after vaccination with 20vPnC for the (SIIV+saline)/20vPnC group

Between-group comparisons will be calculated for local reactions and systemic events specified as following:

- After vaccination with SIIV and 20vPnC for the (SIIV+20vPnC)/saline group vs after vaccination with 20vPnC for the (SIIV+saline)/20vPnC group

5.2.2. Analyses for Continuous Data

Unless otherwise stated, descriptive statistics for continuous variables are n, mean, median, standard deviation, minimum, and maximum.

Continuous immunogenicity outcomes of serotype-specific OPA titers and strain-specific HAI titers will be analyzed on the natural log scale, and the results will be reported on the original scale after exponentiation.

5.2.2.1. Geometric Mean Titers

For immunogenicity results of serotype-specific OPA titers and the strain-specific HAI titers, the geometric means will be computed along with associated 95% CIs. The GMTs and associated 2-sided 95% CIs will be calculated as the means and CIs of the assay results on the natural logarithmic scale based on the t-distribution, and then exponentiating the results.

5.2.2.2. Geometric Mean Ratios

Model-Based GMR

As the primary approach to calculate the GMR and CI for each serotype of OPA titer 1 month after 20vPnC, a linear regression model that includes terms for prior pneumococcal vaccine status, age at vaccination at Visit 1, corresponding baseline OPA titer, sex, smoking status, and vaccine group will be used to calculate the serotype-specific OPA GMR and the associated 95% CI, along with the model-based LS GMTs and associated 2-sided 95% CIs for each vaccine group.

As the primary approach to calculate the GMR and CI for each strain of HAI titer 1 month after SIIV, a linear regression model that includes terms for prior pneumococcal vaccine status, age at vaccination at Visit 1, corresponding baseline HAI titer, sex, smoking status, and vaccine group will be used to calculate the strain-specific HAI GMR and the associated 95% CI, along with the model-based LS GMTs and associated 2-sided 95% CIs for each vaccine group.

CCI [REDACTED]

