4. STUDY DESIGN

4.1. Overall Design

[figure not shown]
This Phase 3, multicenter, randomized, double-blind study, with a 2-arm parallel design, will be conducted at investigator sites in the United States. The purpose of this study is to assess the safety and immunogenicity of 20vPnC and SIIV when given together at the same visit ([SIIV+20vPnC]/saline group) compared to 20vPnC given 1 month after SIIV ([SIIV+saline]/20vPnC group). The study design and assessments are modeled from prior studies of pneumococcal conjugate vaccine coadministered with influenza vaccine.^{68,69,70}

CCI [REDACTED]

Approximately 1780 healthy adults ≥ 65 years of age will be stratified by prior pneumococcal vaccine status (no previous pneumococcal vaccine [naïve], receipt of at least 1 dose of PPSV23 only, receipt of at least 1 dose of 13vPnC only, or receipt of at least 1 dose each of PPSV23 and 13vPnC) and randomized in 1:1 ratio to 1 of 2 groups by center-based randomization. The coadministration group ([SIIV+20vPnC]/saline) will receive SIIV and 20vPnC at the same visit (Visit 1), followed 1 month later by administration of saline (Visit 2). The separate-administration group ([SIIV+saline]/20vPnC) will receive SIIV and saline at Visit 1, followed 1 month later with 20vPnC administered at Visit 2.

Refer to [Section 4.2](#) for the rationale behind this stratification.

If participants have received prior pneumococcal vaccination(s), the most recent dose must have been given ≥ 6 months prior to the first study vaccination. Information on any prior pneumococcal vaccines will be collected at enrollment. **CCI**

On Day 1 (Visit 1), participants will be assessed for eligibility (including medical history and pneumococcal vaccine history). If eligible, participants will have blood drawn for immunogenicity assessments and be randomized to receive either SIIV and 20vPnC ([SIIV+20vPnC]/saline) or SIIV and saline ([SIIV+saline]/20vPnC). The 20vPnC and saline will be prepared and administered by an unblinded investigator site staff member. Participants will be observed for 30 minutes after vaccination by blinded investigator site staff, and any reactions occurring during that time will be recorded as AEs.

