6.3.1. Allocation to Study Intervention

Allocation (randomization) of participants to vaccine groups will proceed through the use of an IRT system (IWR). The site staff (study coordinator or specified designee) will be required to enter or select information, including, but not limited to, the user's ID and password, the protocol number, and the participant number. The site staff will then be

provided with a vaccine assignment, randomization number, and DU or container number when the investigational product is being supplied via the IRT system. The IRT system will provide a confirmation report containing the participant number, randomization number, and DU or container number assigned. The confirmation report must be stored in the site's files.

The study-specific IRT reference manual and IP manual will provide the contact information and further details on the use of the IRT system.

Participants will be stratified by prior pneumococcal vaccine status (no previous pneumococcal vaccine [naïve], receipt of at least 1 dose of PPSV23 only or at least 1 dose of 13vPnC only, or receipt of at least 1 dose of both PPSV23 and 13vPnC) and randomized in a 1:1 ratio to each of the 2 vaccine groups, either the coadministration group ([SIIV+20vPnC]/saline) or the separate-administration group ([SIIV+saline]/20vPnC group), by center-based randomization. Investigators will remain blinded to each participant's assigned study intervention throughout the course of the study. In order to maintain this blind, an otherwise uninvolved third party will be responsible for the preparation and dispensing of all study intervention and will endeavor to ensure that there are no differences in time or effort taken to administer the study intervention and no blinded site staff are able to view the administration.

This third party will instruct the participant to avoid discussing the packaging of the study intervention with the investigator.

In the event of a Quality Assurance audit, the auditor(s) will be allowed access to unblinded study intervention records at the site(s) to verify that randomization/dispensing has been done accurately.

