9.1.3. Multiplicity Considerations

For the primary immunogenicity assessment of NI of coadministration of SIIV and 20vPnC ([SIIV+20vPnC]/saline group) to administration of SIIV followed by 20vPnC 1 month later ([SIIV+saline]/20vPnC group) for all 20 OPA serotypes in 20vPnC and all the HAI strains in SIIV, a 2-sided test for each of the 20 OPA serotypes and each of the HAI strains is performed only once at an alpha level of 0.05. The primary immunogenicity objectives of the study will be achieved if the 2-fold NI criterion is met for each of the 20 OPA serotypes and the 1.5-fold NI criterion is met for each of the HAI strains. Therefore, the type I error rate for the immunogenicity assessments is well controlled.

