9.2. Sample Size Determination

CCI

Sample size and power are based on simulations with assumptions supported by the OPA results from a Phase 3 pivotal study (B7471007) of 20vPnC and a Phase 4 study (B1851138) of 13vPnC evaluating the immune response when 13vPnC was given concomitantly and separately. With 800 evaluable participants in each vaccine group, the study has approximately 99%, 95%, and 75% power to demonstrate NI for at least 18 out of 20, for at least 19 out of 20, and for all 20 serotypes, respectively. Assuming a nonevaluable rate of 10%, the study will randomize approximately 1780 participants to achieve 800 evaluable participants in each group.

CCI

[REDACTED]

[REDACTED]	[REDACTED]	+	[REDACTED]
[REDACTED]	[REDACTED]	[REDACTED]	[REDACTED]
[REDACTED]	[REDACTED]	[REDACTED]	[REDACTED]
[REDACTED]	[REDACTED]	[REDACTED]	[REDACTED]
[REDACTED]	[REDACTED]	[REDACTED]	[REDACTED]
[REDACTED]	[REDACTED]	[REDACTED]	[REDACTED]
[REDACTED]	[REDACTED]	[REDACTED]	[REDACTED]
[REDACTED]	[REDACTED]	[REDACTED]	[REDACTED]
[REDACTED]	[REDACTED]	[REDACTED]	[REDACTED]
[REDACTED]	[REDACTED]	[REDACTED]	[REDACTED]
[REDACTED]	[REDACTED]	[REDACTED]	[REDACTED]
[REDACTED]	[REDACTED]	[REDACTED]	[REDACTED]
[REDACTED]	[REDACTED]	[REDACTED]	[REDACTED]
[REDACTED]	[REDACTED]	[REDACTED]	[REDACTED]
[REDACTED]	[REDACTED]	[REDACTED]	[REDACTED]
[REDACTED]	[REDACTED]	[REDACTED]	[REDACTED]
[REDACTED]	[REDACTED]	[REDACTED]	[REDACTED]
[REDACTED]	[REDACTED]	[REDACTED]	[REDACTED]
[REDACTED]	[REDACTED]	[REDACTED]	[REDACTED]
[REDACTED]	[REDACTED]	[REDACTED]	[REDACTED]
[REDACTED]	[REDACTED]	[REDACTED]	[REDACTED]
[REDACTED]	[REDACTED]	[REDACTED]	[REDACTED]
[REDACTED]	[REDACTED]	[REDACTED]	[REDACTED]
[REDACTED]	[REDACTED]	[REDACTED]	[REDACTED]
[REDACTED]	[REDACTED]	[REDACTED]	[REDACTED]
[REDACTED]	[REDACTED]	[REDACTED]	[REDACTED]
[REDACTED]	[REDACTED]	[REDACTED]	[REDACTED]
[REDACTED]	[REDACTED]	[REDACTED]	[REDACTED]
[REDACTED]	[REDACTED]	[REDACTED]	[REDACTED]
[REDACTED]	[REDACTED]	[REDACTED]	[REDACTED]
[REDACTED]	[REDACTED]	[REDACTED]	[REDACTED]
[REDACTED]	[REDACTED]	[REDACTED]	[REDACTED]
[REDACTED]	[REDACTED]	[REDACTED]	[REDACTED]
[REDACTED]	[REDACTED]	[REDACTED]	[REDACTED]
[REDACTED]	[REDACTED]	[REDACTED]	[REDACTED]
[REDACTED]	[REDACTED]	[REDACTED]	[REDACTED]
[REDACTED]	[REDACTED]	[REDACTED]	[REDACTED]
[REDACTED]	[REDACTED]	[REDACTED]	[REDACTED]
[REDACTED]	[REDACTED]	[REDACTED]	[REDACTED]
[REDACTED]	[REDACTED]	[REDACTED]	[REDACTED]
[REDACTED]	[REDACTED]	[REDACTED]	[REDACTED]

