[REDACTED]	[REDACTED]	[REDACTED]	[REDACTED]
[REDACTED]	[REDACTED]	[REDACTED]	[REDACTED]
[REDACTED]	[REDACTED]	[REDACTED]	[REDACTED]
[REDACTED]	[REDACTED]	[REDACTED]	[REDACTED]

CCI

[REDACTED]

CCI [REDACTED] Assuming the GMR of the (SIIV+20vPnC)/saline group to the (SIIV+saline)/20vPnC group is 0.9 for each HAI strain and standard deviations are the same as those observed in Study B1851138, 800 evaluable participants in each vaccine group provide approximately 99% power to demonstrate NI for all HAI strains.

CCI [REDACTED]

[REDACTED]	[REDACTED]	[REDACTED]	[REDACTED]
[REDACTED]	[REDACTED]	[REDACTED]	[REDACTED]
[REDACTED]	[REDACTED]	[REDACTED]	[REDACTED]
[REDACTED]	[REDACTED]	[REDACTED]	[REDACTED]
[REDACTED]	[REDACTED]	[REDACTED]	[REDACTED]

[REDACTED]

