9.4.1. Immunogenicity Analysis

The statistical analysis of immunogenicity results will be primarily based on the evaluable immunogenicity populations as defined in Section 9.3.

CCI [Redacted]

Missing serology results will not be imputed. Titers below LLOQ or denoted as BLQ will be set to $0.5 \times \text{LLOQ}$ for analysis.

Endpoint	Statistical Analysis Methods
Primary pneumococcal immunogenicity	
 For the 20 serotypes in 20vPnC, 1 month after vaccination refers to 1 month after vaccination with 20vPnC and SIIV (Visit 2) for the (SIIV+20vPnC)/saline group and 1 month after vaccination with 20vPnC (Visit 3) for the (SIIV+saline)/20vPnC group. For each of the 20 serotype-specific OPA titers, the GMRs of the (SIIV+20vPnC)/saline group GMT to the (SIIV+saline)/20vPnC group GMT at 1 month after vaccination will be provided. GMRs and their 2-sided 95% CIs will be derived by calculating differences in means and CIs on the natural log scale, then exponentiating the results. The difference in means, on the natural log scale, will be the (SIIV+20vPnC)/saline group at Visit 2 minus the (SIIV+saline)/20vPnC group at Visit 3 for the 20 serotypes in 20vPnC. 
As the primary approach to calculate the GMR and CI for each serotype of OPA titer, a linear regression model that includes terms for prior pneumococcal vaccine status, age (at the time of randomization), corresponding baseline OPA titer, sex, smoking status, and vaccine group will be used to calculate the serotype-specific OPA GMR and 95% CI, along with the model-based least squares GMTs and associated 2-sided 95% CIs for each vaccine group. NI for a serotype will be declared if the lower bound of the 2-sided 95% CI for the GMR of the (SIIV+20vPnC)/saline group over the (SIIV+saline)/20vPnC group exceeds 0.5. CCI [Redacted]
 
CCI [Redacted]

	
This analysis will be based on the evaluable pneumococcal immunogenicity populations in order to provide a comparison that has the greatest chance of identifying a difference between the groups with respect to immunogenicity, if a meaningful difference in vaccine effect actually exists.

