Primary SIIV immunogenicity	
• For the HAI strains in SIIV, 1 month after vaccination refers to 1 month after vaccination with SIIV (Visit 2) for both vaccine groups.• For each of the HAI strains, the GMRs of the (SIIV+20vPnC)/saline group GMT to the (SIIV+saline)/20vPnC group GMT at 1 month after vaccination will be provided. GMRs and their 2-sided 95% CIs will be derived by calculating differences in means and CIs on the natural log scale, then exponentiating the results. The difference in means, on the natural log scale, will be the (SIIV+20vPnC)/saline group at Visit 2 minus the (SIIV+saline)/20vPnC group at Visit 2 for all HAI strains in SIIV. 
As the primary approach to calculate the GMR and CI for each strain of HAI titer, a linear regression model that includes terms for prior pneumococcal vaccine status, age (at the time of randomization), corresponding baseline HAI titer, sex, smoking status, and vaccine group will be used to calculate the strain-specific HAI GMR and 95% CI, along with the model-based least squares GMTs and associated 2-sided 95% CIs for each vaccine group. NI for a strain will be declared if the lower bound of the 2-sided 95% CI for the GMR of the (SIIV+20vPnC)/saline group over the (SIIV+saline)/20vPnC group exceeds 0.67. CCI [REDACTED]
 
CCI [REDACTED]
 
This analysis will be based on the evaluable HAI immunogenicity populations in order to provide a comparison that has the greatest chance of identifying a difference between the groups with respect to immunogenicity, if a meaningful difference in vaccine effect actually exists.

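### Allocation is by center, but both primary NI models leave center out; if allocation is balanced within centers that differ, the GMR intervals are slightly too wide and the tests slightly conservative

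*SAP*

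**What the plan says.** Protocol 4.1 stratifies participants by prior pneumococcal vaccine status and has them "randomized in 1:1 ratio to 1 of 2 groups by center-based randomization". Protocol 6.3.1 ends its allocation sentence the same way: "the separate-administration group ([SIIV+saline]/20vPnC group), by center-based randomization". SAP 2.2 repeats the scheme. None of these places gives the block size, the number of centers or the balancing rule.

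The primary OPA model in SAP 5.2.2.2 is a "linear regression model that includes terms for prior pneumococcal vaccine status, age at vaccination at Visit 1, corresponding baseline OPA titer"; its other terms are vaccine group, smoking status and sex. Protocol 9.4.1 has the same list for OPA ("corresponding baseline OPA titer, sex, smoking status, and vaccine group will be used to calculate the serotype-specific OPA GMR and 95% CI") and for HAI ("corresponding baseline HAI titer, sex, smoking status, and vaccine group will be used to calculate the strain-specific HAI GMR and 95% CI"). SAP 6.1.2.1.1 and 6.1.2.2.1 repeat both lists. Center appears in none of them, and no visible text says why. Some text after the models is blacked out, but the term lists are complete before it, and a hidden supplementary analysis would not change the primary terms.

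Protocol 9.1.3 sets the success rule: "The primary immunogenicity objectives of the study will be achieved if the 2-fold NI criterion is met for each of the 20 OPA serotypes". Every HAI strain must also meet the 1.5-fold criterion. On power, Protocol 9.2 says "the study has approximately 99%, 95%, and 75% power to demonstrate NI" for at least 18, at least 19 and all 20 serotypes respectively. For influenza, "800 evaluable participants in each vaccine group provide approximately 99% power to demonstrate NI for all HAI strains".

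**The concern.** The plan restricts allocation by two factors and adjusts for only one. When treatment is balanced within center, differences between centers largely cancel out of the group contrast, so the GMR is more precise than under simple randomization. A regression without center leaves those differences in its residual variance and reports a standard error that is too large. The lower confidence limit then sits too low, and NI is declared slightly less often than the data warrant.

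This cannot produce a false NI claim. What is at stake is power, and it matters mainly for OPA: all 20 serotypes must pass, and the sponsor's own assumptions leave about one chance in four of missing that.

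**Working it through.** **Inputs from the documents.** About 1780 randomized, 10% nonevaluable, 800 evaluable per group; margins 0.5 (OPA) and 0.67 (HAI); lower limit of a two-sided 95% CI; HAI GMR of 0.9 assumed; power 99/95/75% for OPA and 99% for HAI (Protocol 9.1.2, 9.1.3, 9.2). SAP 3.1.3 names four strains.

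**Inputs assumed.** Share *r* of residual variance due to center (the ICC): 2%, 5%, 10%. Centers: 30, 60 or 120, unequal in size. Permuted blocks of 4 within center by stratum, with four strata as in Protocol 4.1.

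**Plan's own figure.** 1600 / 0.9 = 1778, which agrees with 1780. The OPA power rests on simulation inputs that are blacked out, so it cannot be rerun. HAI power of 99% for all four strains (taken as independent) needs a log-scale SD of about 1.24 or less; the actual SDs are not visible.

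**Analytic effect under full balance.** Model SE without center / true SE ≈ 1/√(1 − *r*), and one-sided alpha = 1 − Φ(1.96/√(1 − *r*)).

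| *r* | SE ratio | one-sided alpha |
|---|---|---|
| 2% | 1.010 | 0.024 |
| 5% | 1.026 | 0.022 |
| 10% | 1.054 | 0.019 |

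**Simulation with incomplete blocks and 10% loss** (60 centers, unit total residual variance, 1000 replicates):

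| *r* | model SE, no center | model SE, random intercept | ratio | true SE, no center | model / true, no center |
|---|---|---|---|---|---|
| 2% | 0.05001 | 0.04959 | 1.008 | 0.04959 | 1.008 |
| 5% | 0.04994 | 0.04879 | 1.024 | 0.04897 | 1.020 |
| 10% | 0.04987 | 0.04751 | 1.050 | 0.04793 | 1.040 |

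Over 30 to 120 centers, the intervals without center are wider by 0.8-0.9%, 2.1-2.4% and 4.7-5.0%; at *r* = 0 the difference is about 0.1%. A separate 4,000-run simulation with 30 centers and fixed center effects gave SE ratios of 1.008, 1.023 and 1.050. At *r* = 10% its one-sided alpha was 0.019 without center and 0.025 with it.

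**Fixed versus random.** With 120 centers, unpooled fixed effects widen the interval by 1.6% at *r* = 0 and 0.6% at *r* = 2%.

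**Power for one weak serotype, as an illustration.** Assume a true GMR of 0.75, SD 2.5 and *r* = 10%. The distance to the margin is ln(0.75/0.5) = 0.4055; model SE = 2.5 × √(2/800) = 0.125; true SE = 0.125 × √0.9 = 0.1186.
- Without center: Φ((0.4055 − 1.96 × 0.125)/0.1186) = 91.2%.
- With center: Φ((0.4055 − 1.96 × 0.1186)/0.1186) = 92.8%.

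**Power for all 20.** Equicorrelated normal test statistics were set to reproduce about 99/95/75%, with 3, 5, 10 or 20 limiting serotypes (correlation 0.3, 0.18, 0.1, 0.1). The center term adds about 0.5-1.0, 1.6-2.6 and 3.5-5.3 points at *r* = 2%, 5% and 10%. Example with 20 limiting serotypes, 60 centers and *r* = 10%: 75% rises to 80.3% if 75% is the actual power of the model without center; 79.6% rises to 84.2% if the 75% was worked out from the total SD.

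**HAI.** At SD 1.25 and GMR 0.9, the lower limit is 0.9 × exp(−1.96 × 0.0625) = 0.796 without center. With it, the limit is 0.797, 0.799 or 0.801 at *r* = 2%, 5% or 10%. All-strain power at *r* = 10% moves from 99.0% to 99.3%.

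**The case against.** The planned analysis is valid. It is unbiased and errs toward conservatism, it applies one simple model to all 24 comparisons (20 serotypes and 4 strains), and it already adjusts for the named stratification factor and each participant's own baseline titer. All of that stands, and it is why the point is minor.

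The conservatism needs balance within center, which the documents never spell out. That also stands: with no blocking by center and *r* = 10%, the ratio of model to true SE was 1.00 and alpha 0.026. It does not remove the gain, though. In that setting a random intercept still lowered the SE from 0.0499 to 0.0480, because it removes real between-center variation.

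The size is assumed. US-only sites, a single proposed SIIV lot and baseline adjustment may keep center effects small, and at *r* = 2% the interval changes by under 1%. The power gains use inputs chosen to match the stated 99/95/75%, and under one reading of the 75% the present model already exceeds it. These points limit how firmly the gain can be stated, not its direction.

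A mixed model also needs a degrees-of-freedom method, and a fallback that depends on the data could leave different serotypes with different models. Both can be handled by prespecification. When the center variance is estimated as zero, the fallback is just the current model.

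**Conclusion.** The concern holds, as a minor loss of precision. The primary OPA and HAI models omit a factor used in allocation. If allocation is balanced within center and centers differ after the covariates, the GMR intervals are somewhat too wide: by about 1% at an assumed residual center share of 2%, and about 5% at 10%. For OPA this is worth from about half a point to about five points of all-20 power; for HAI it is negligible. The number of centers, the block size and the center share are all assumptions, and the upper end of the range is hypothetical. The stated sample size does not depend on this point.

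**What to change.** Before unblinding, add center as a random intercept to the OPA model, and to the HAI model for consistency, in Protocol 9.4.1 and SAP 5.2.2.2, 6.1.2.1.1 and 6.1.2.2.1. Name the degrees-of-freedom method. State that any comparison whose center variance is estimated as zero, or whose fit fails, reverts to the current model. Keep all other terms and both NI criteria. Avoid unpooled fixed center effects, which can widen the interval when there are many small centers. It would also help to say in Protocol 6.3.1 whether allocation is balanced within center.

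The cost is one model term and a short fallback rule, with a mixed model replacing ordinary regression. Protocol 9 and SAP 2 require a protocol amendment for major modifications of the primary analysis; if the sponsor classes this as one, that step is the larger part of the cost. If the sponsor prefers to keep the present model, the SAP should at least say why center is left out.
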